8.2 Potential Benefits

The subjects may or may not benefit from the treatment with the study device. Potential benefit is improved appearance of treated area. There is no guarantee of success.

9 DATA ANALYSIS PLAN

9.1 Sample Size

This is an efficacy and safety study on an approved device and 40 subjects has been deemed appropriate for evaluation of the device.

9.2 Analysis Sets

The analysis sets will include all enrolled subjects who complete treatment.

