4 STUDY DESIGN

This is a multi-center, study in approximately 50 subjects, age 18 and older. . Subjects may receive [REDACTED] treatments and will be followed at 4 and 12 weeks post the final treatment. [REDACTED]

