4.1.2 Safety Endpoints

- Incidence and severity of adverse device events.

4.1.3 [REDACTED]

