4.2 Study Duration

Subjects enrolled in this trial will be asked to participate for approximately 8 months, depending on treatment(s).

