4.3.2 Safety Assessments

Following the first treatment, adverse events (AEs) will be assessed post-treatment and at each subsequent visit using the following scale:

- 1= mild: requires minimal or no treatment and does not interfere with the subject's daily activities.
- 2= moderate: may cause some interference with functioning.
- 3= severe: interrupts subject's usual daily activity and may require treatment.

Treatment-related Discomfort:

After each treatment, subjects will be asked to rate the average amount of discomfort experienced during treatment and immediately after treatment using the Pain Rating Scale (VAS Scale) Appendix 2.

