5.2.1 Subject Discontinuation Criteria

If possible, every subject should remain in the study until completion of the required follow-up period. However, participation in this study is completely voluntary and a subject can choose to withdraw from the study at any time. Decision to withdraw will not affect or prejudice the subject's continued medical care in any way. In those instances, the investigator will attempt to obtain a final clinical assessment and an adverse device effect evaluation for the subject prior to this withdrawal. A subject will be considered lost to follow-up only after three unsuccessful, documented attempts to contact the subject have been made.

In addition, a subject can be discontinued for any of the following reasons: the Principal Investigator decides that continuing in the study would not be in the subject's best interest, a subject is noncompliant with the protocol, a subject has a serious reaction to the treatment, a subject develops any of the exclusion criteria during the study period or the study is stopped by the study sponsor.

[REDACTED]

[REDACTED]

[REDACTED]

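### If treatment runs to more than one session, the completers-only rule in 9.2 can drop subjects stopped for a serious reaction from the adverse-event percentages in 9.4

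*Protocol*

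**What the plan says.** Section 9.2 consists of one sentence: "The analysis sets will include all enrolled subjects who complete treatment". It speaks of sets in the plural but describes a single group. Section 9.4 plans a descriptive table of device- and procedure-related adverse events, counted by subject within each term, with numbers and percentages. It names no population of its own. Sections 9.1 to 9.4 are all readable, and none carries a redaction mark.

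The safety endpoint in 4.1.2 is "Incidence and severity of adverse device events". Among the grounds for discontinuing a subject, 5.2.1 lists that "a subject has a serious reaction to the treatment".

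The number of treatments is redacted in section 4, and the readable text does not say what counts as completing treatment. The visible wording suggests repeated sessions. Under section 4 subjects "will be followed at 4 and 12 weeks post the final treatment". Section 4.3.2 says "Following the first treatment, adverse events (AEs) will be assessed post-treatment and at each subsequent visit", and also "After each treatment, subjects will be asked to rate the average amount of discomfort experienced during treatment". Section 4.2 gives a participation time of about 8 months, but it writes treatment with an optional plural.

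**The concern.** A safety population should be fixed by exposure, not by how the subject fared afterwards. Under 9.2 as written, a subject who has one session, reacts badly and is stopped before the next is not a completer. That subject is then missing from the only adverse-event summary that the visible analysis section plans. The people most likely to be removed are those whose reactions the safety endpoint exists to count. The table could therefore understate both the incidence and the severity of the reactions that led to stopping.

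The event itself is not lost. Section 7.2 requires it to be recorded in the case report form and, if serious, reported to the sponsor. What is at stake is the summarised incidence and severity.

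**Working it through.** The protocol states no rate, so it has no figure to reproduce. The 40 in section 9.1 is a judgement without a calculation. The check has three parts.

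**1. Does the text lead to exclusion?** Section 9.2 limits the sets to subjects who finish treatment, 9.4 supplies no alternative, and 5.2.1 lets a serious reaction end a subject's participation. Taken together, a subject stopped between sessions is outside the 9.4 table. A subject who reacts after the last session stays in, because treatment is then complete. The mechanism therefore needs more than one session.

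**2. Is more than one session likely?** The references to a first, each and a final treatment (sections 4 and 4.3.2) point that way. The duration gives weaker support:

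- 8 months = 8 × 365.25 / 12 / 7 = 34.8 weeks (section 4.2)
- less the 12 weeks of follow-up after the final treatment (section 4): 34.8 − 12 = 22.8 weeks, about 23

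Some of that time may be screening and visit windows, so this is not a treatment-phase length. It fits repeated sessions without proving them.

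**3. How large could the effect be?** Let N be the number treated, k the number stopped early for a given reaction, and c the number of completers who also have it.

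- All treated subjects: (c + k) / N
- Completers only, as in 9.2: c / (N − k)
- Difference: (c + k)/N − c/(N − k) = k(N − k − c) / [N(N − k)]

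Since c cannot exceed N − k, the difference is never negative. For the reaction that caused the stopping, the completers-only figure can only be too low, or equal if every completer also has it.

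N is taken as 40 (section 9.1) or about 50 (section 4). The values of k and c are assumptions for illustration.

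| N | k | c | All treated | Completers only |
|---|---|---|---|---|
| 40 | 1 | 0 | 1/40 = 2.5% | 0/39 = 0% |
| 40 | 2 | 0 | 2/40 = 5.0% | 0/38 = 0% |
| 40 | 2 | 1 | 3/40 = 7.5% | 1/38 = 2.6% |
| 40 | 2 | 2 | 4/40 = 10.0% | 2/38 = 5.3% |
| 40 | 5 | 0 | 5/40 = 12.5% | 0/35 = 0% |
| 50 | 2 | 0 | 2/50 = 4.0% | 0/48 = 0% |
| 50 | 5 | 0 | 5/50 = 10.0% | 0/45 = 0% |

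A term that the stopped subjects did not have moves slightly the other way. With N = 40, 2 stopped without the term and 2 completers with it, 2/40 = 5.0% becomes 2/38 = 5.3%. If k = 0, the two populations give the same figure.

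**The case against.** The strongest objection is that the mechanism runs through redacted text. The number of sessions is blacked out, the study-procedures section that might define completion is not visible, and the optional plural in 4.2 leaves a single session possible. This stands, and it is why the point is conditional. With a single session, few or no treated subjects would be affected.

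Second, 9.2 says that the sets include completers; it does not say that they include only completers. Since 9.4 does not refer back to 9.2, the table could be run on all treated subjects without open contradiction, and a separate statistical analysis plan might define a safety set. That reading is possible. But no other set is named, and a programmer who applied 9.2 as written would arrive at completers. The protocol has not left the population open. It has stated a rule, and an analysis plan using all treated subjects would have to depart from it.

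Third, the consequence is limited. Section 5.2.1 permits discontinuation for a serious reaction but does not require it. The device is described as approved, no formal testing is planned, serious events reach the sponsor within 5 working days, and every count of stopped subjects above is assumed. All of this is true. It bounds the harm to a descriptive summary of unknown error, but that summary is the planned analysis of the stated safety endpoint.

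**Conclusion.** The concern holds. As written, 9.2 and 9.4 together allow subjects to be left out of the safety summary because of the outcome that it counts. For the reactions that cause stopping, the error runs only towards better apparent safety.

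The size cannot be determined from the protocol. In a study of 40 to 50 subjects, one or two early stops are enough to turn a rate of 2% to 5% (1/50 to 2/40) into 0% when no completer has the same reaction. The conclusion assumes a course of more than one session, completion meaning receipt of the whole course, and at least one subject stopped before the end because of a reaction. If any of these fails, the effect is small or nil. Confidence is medium for that reason. The wording should still be corrected, because it bears on a stated endpoint and is easy to put right.

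**What to change.** In 9.2, define a safety set of every subject who received any part of at least one Secret RF treatment. In 9.4, state that all adverse-event tabulations use that set. The completer set may stay for efficacy.

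The cost is one sentence in 9.2 and a reference in 9.4. No new data are needed, because 4.3.2 and 7.2 already collect adverse events from the first treatment onward. For subjects who choose to withdraw, 5.2.1 adds that "the investigator will attempt to obtain a final clinical assessment and an adverse device effect evaluation for the subject prior to this withdrawal". That sentence concerns voluntary withdrawal and is not repeated for subjects discontinued for a reaction, so the argument rests on 4.3.2 and 7.2. The only downside for the sponsor is that some adverse-event percentages may look slightly less favourable.

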9.3 Analysis of Efficacy/Exploratory Endpoints

Formal hypothesis testing and statistical analysis are not planned for this study.

9.4 Safety Analyses

Device-related and procedure-related adverse effects (AEs) will be tabulated and analyzed. For a given AE term, counting will be done by subject, not by event, i.e. for a subject reporting the same AE more than once, the event will be counted only once, at the most severe and longest duration. The number and percentage of subjects experiencing each AE Term will be descriptively summarized.

10 STUDY MANAGEMENT AND ADMINISTRATIVE PROCEDURES

[REDACTED]

[REDACTED]

[REDACTED]

[REDACTED]

[REDACTED]

[REDACTED]

[REDACTED]

10.3 Protocol Compliance

The principal investigator must comply with all terms of the protocol.

10.3.1 Protocol Amendments

Neither the principal investigator nor the sponsor will modify or alter this protocol without first obtaining the concurrence of the other party (with the exception of amendments which involves mitigating a medical emergency or immediate health risk to the subject). The party initiating an amendment must confirm it clearly in writing and it must be signed and dated by the sponsor and the principal investigator. IRB approval must be obtained before implementation of an amendment.

10.3.2 Protocol Deviations

All protocol deviations must be clearly described on the case report form (i.e., Cutera Protocol Deviation Form). Deviations from the protocol may include but are not limited to subject's failure to attend scheduled visit during a visit window, and incomplete or incorrect study procedures. Any medical emergency or immediate health risk to the subject which results in a protocol deviation and must be reported to the sponsor within 5 working days

Significant protocol deviations must be reported to IRB according to their policies.

[REDACTED]

[REDACTED]

[REDACTED]

10.5 Subject Confidentiality

This study preserves the confidentiality of all subjects under the Health Insurance Portability and Accountability Act of 1996 (HIPAA) Privacy Rule. The following safeguards will be in place to protect the privacy of the individuals who are the subjects of the health information to be used in the research and the confidentiality of that information:

[REDACTED]

[REDACTED]

[REDACTED]

[REDACTED]

10.6 Publication Policy

The investigator shall have the right to publish the results of the study. Unless mutually agreed upon in writing, prior to submission for publication of any manuscript, poster, presentation, abstract or other written or oral material describing the results of the study, the investigator shall allow sponsor to review manuscript, poster presentation, abstract or other written or oral material which describes the results of the study for the purpose only of determining if any patentable information is disclosed. At the sponsor's request, the investigator shall withhold any publication or presentation to permit sponsor to seek patent protection and to remove any confidential information from all publications.

[REDACTED]

[REDACTED]

[REDACTED]

[REDACTED]

[REDACTED]

[REDACTED]

[REDACTED]

[REDACTED]

[REDACTED]

[REDACTED]

[REDACTED]	[REDACTED]	[REDACTED]	[REDACTED]	[REDACTED]
[REDACTED]	[REDACTED]	[REDACTED]	[REDACTED]	[REDACTED]
[REDACTED]	[REDACTED]	[REDACTED]	[REDACTED]	[REDACTED]
[REDACTED]	[REDACTED]	[REDACTED]	[REDACTED]	[REDACTED]
[REDACTED]	[REDACTED]	[REDACTED]	[REDACTED]	[REDACTED]
[REDACTED]	[REDACTED]	[REDACTED]	[REDACTED]	[REDACTED]
[REDACTED]	[REDACTED]	[REDACTED]	[REDACTED]	[REDACTED]
[REDACTED]	[REDACTED]	[REDACTED]	[REDACTED]	[REDACTED]
[REDACTED]	[REDACTED]	[REDACTED]	[REDACTED]	[REDACTED]
[REDACTED]	[REDACTED]	[REDACTED]	[REDACTED]	[REDACTED]
[REDACTED]	[REDACTED]	[REDACTED]	[REDACTED]	[REDACTED]
[REDACTED]	[REDACTED]	[REDACTED]	[REDACTED]	[REDACTED]

[REDACTED]

[REDACTED]

[REDACTED]

[figure not shown]
[REDACTED]

[REDACTED]

[figure not shown]
[REDACTED]

[Redacted text block]

[Redacted text block]

[Redacted text block]

[Redacted text block]

[Redacted text block]

[Redacted text block]
